1.2 Schema

Description of Study

This is a Phase 1b/2a, open-label, multicenter study to evaluate the safety, tolerability and anti-tumor effect of NT-I7 (recombinant human interleukin 7 [rhIL]-7-hybrid Fc [hyFc]) in combination with atezolizumab (MPDL3280A) in patients with anti-PD-1/PD-L1 naïve or relapsed/refractory high-risk skin cancers including cSCC, MCC and melanoma.

This study has been designed to allow for an investigation of MTD or RP2D of NT-I7 in combination with atezolizumab. There are two phases to this study:

[figure not shown]
- Phase 1b, a NT-I7 dose-escalation phase to determine the MTD or RP2D
- Phase 2a, a non-randomized parallel dose expansion phase to confirm the MTD or RP2D in both arms.

Arm I: Anti-PD-1/PD-L1 (checkpoint inhibitors [CPI]) naïve patients with cSCC and MCC

Arm II: Anti-PD-1/PD-L1 relapsed/refractory patients with MCC, cSCC and melanoma

Number of Patients

A total of approximately 84 patients will be enrolled; up to approximately 24 patients will be enrolled in the Phase 1b (3 + 3 dose escalation design will be used), and approximately 60 patients will be enrolled in the Phase 2a (24 patients in Arm I, i.e., 12 patients for each indication, and 36 patients in Arm II, i.e., 12 patients for each indication).

[figure not shown]

*Each cohort includes checkpoint inhibitor (CPI) naïve and relapsed/refractory patients with high-risk skin cancer; n=3 or 6 based on the 3+3 study design

^aNT-I7 Dose Interruption

NT-I7 administration will be skipped when the ALC is higher than 10,000 cells/µL on Day 1 of every other cycle, starting on Cycle 3. Blood draws conducted prior to dosing on Day 1 will determine if NT-I7 should be interrupted for the current cycle.

^bStarting with DL4 (1200 µg/kg), NT-I7 dosing is changed from Q3W to Q6W. Atezolizumab dosing remains the same (Q3W).

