3. OBJECTIVES AND ENDPOINTS

This study will evaluate the safety and tolerability and assess the antitumor efficacy of NT-I7 in combination with atezolizumab (Phase 1b/2a) in patients with anti-PD-1/PD-L1 naïve or relapsed/refractory high-risk skin cancers (cSCC, MCC, melanoma). Specific objectives and corresponding endpoints for the study are outlined in Table 2.

Table 2 – Study Objectives and Endpoints

Objectives	Corresponding Endpoints
Primary Objective	

To evaluate the safety and tolerability of NT-I7 in combination with atezolizumab (Phase 1b), including estimation of the Maximum Tolerated Dose (MTD) and/or the Recommended Phase 2 Dose (RP2D)
 
Phase 2a: To evaluate the Objective Response Rate (ORR) according to RECIST v1.1 and iRECIST, as determined by the investigator
	
 - Incidence, nature, and severity of adverse events graded according to NCI CTCAE v5.0 - Incidence and nature of DLTs - Potential correlation with PK, pharmacodynamic, safety, and efficacy parameters - Objective Response Rate (ORR), defined as the percentage of patients who have at least one confirmed partial response (PR) or complete response (CR) according to RECIST v1.1 and iRECIST, as determined by the investigator
Secondary Objectives	

To evaluate immunogenicity of NT-I7 in combination with atezolizumab
 
To make a preliminary assessment of the anti-tumor activity of NT-I7 in combination with atezolizumab
	
 - Incidence of anti-drug antibody (ADA) to NT-I7 during the study relative to the prevalence of ADA at baseline - Disease Control Rate (DCR), defined as proportion of patients with a best overall response of CR, PR or stable disease (SD). - Duration of objective response (DOR), defined as the time from the first occurrence of a documented objective response to the time of the first documented disease progression or death from any cause, whichever occurs first, per RECIST v1.1 and iRECIST as determined by the investigator - Progression Free Survival (PFS), defined as the time from the first study treatment (Cycle 1, Day 1) to the first occurrence of progression or death from any cause, whichever occurs first, per RECIST v1.1 and iRECIST as determined by the investigator - Overall survival (OS), defined as the time from first study treatment (Cycle 1, Day 1) to death from any cause
Exploratory Objectives	

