5.1 Overall Design

This is a Phase 1b/2a, non-randomized 2 arm, open label multi-institutional trial. The dose escalation phase (Phase 1b) of the study will determine the MTD or RP2D of NT-I7 in combination with atezolizumab. The Phase 2a will be a non-randomized parallel dose expansion phase to confirm the MTD or RP2D in both arms.

A total of approximately 84 patients will be enrolled; up to approximately 24 patients will be enrolled in the Phase 1b (a 3+3 dose escalation design will be used), and approximately 60 patients will be enrolled in the Phase 2a (24 patients in Arm I, i.e., 12 patients for each indication, and 36 patients in Arm II, i.e., 12 patients for each indication).

Arm I: Anti-PD-1/PD-L1 (CPI) naïve patients with cSCC and MCC

[figure not shown]
Arm II: Anti-PD-1/PD-L1 relapsed/refractory patients with MCC, cSCC and melanoma

^aNT-I7 Dose Interruption

NT-I7 administration will be skipped when the ALC is higher than 10,000 cells/µL on Day 1 of every other cycle, starting on Cycle 3. Blood draws conducted prior to dosing on Day 1 will determine if NT-I7 should be interrupted for the current cycle.

^bStarting with DL4 (1200 µg/kg), NT-I7 dosing is changed from Q3W to Q6W. Atezolizumab dosing remains the same (Q3W).

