6.2.2 Non-hematologic toxicity

Any Grade ≥ 3 non-hematologic toxicity (Common Terminology Criteria for Adverse Events [CTCAE] v5.0) will be considered a DLT, **except** for the following, which will not constitute DLTs:

- Grade ≥ 3 nausea, diarrhea or vomiting that resolves to Grade ≤ 2 in ≤ 72 hours with the use of adequate/maximal medical intervention and/or prophylaxis
- Grade 3 fatigue that resolves to Grade ≤ 2 in ≤ 7 days
- Grade 3 fever
- Grade 3 injection site reaction (unless operative intervention is required)
- Grade 3 arthralgia that can be adequately managed with supportive care or that resolves to Grade ≤ 2 within ≤ 72 hours
- Grade 3 hyperglycemia lasting ≤ 72 hours with standard antidiabetic therapy

- Grade 3 autoimmune thyroiditis or other disorder that can be managed by endocrine therapy that would not necessitate initiation of systemic corticosteroids (except for mineralocorticoids (e.g., fludrocortisone) for adrenocortical insufficiency)
- Grade ≥ 3 amylase or lipase that is not associated with symptoms or clinical manifestations of pancreatitis and resolves to \leq Grade 1 within 7 days
- Grade ≥ 3 electrolyte abnormalities that last ≤ 72 hours, is not clinically complicated, and resolves spontaneously or responds to conventional medical interventions
- Clinical laboratory abnormalities that are reversible to \leq Grade 1 within 72 hours with outpatient care and/or monitoring, and are not considered clinically significant by the treating physician

Management and dose modifications associated with the above AEs are outlined in Section 7.

Once all patients in a cohort have completed the 3-week (21 days) DLT window, the AEs will be assessed by the Data and Safety Monitoring Committee, which includes the PI(s), study Sponsor and the ION Coordinating Center.

The patients must complete the full 3-week DLT window to be considered evaluable for DLTs. Patients who discontinue from the study before completion of the full 3-week DLT window for reasons other than the occurrence of a DLT (e.g., withdrawal of consent, rapid tumor progression, death due to rapid tumor progression, AE that does not meet DLT criteria) will not be considered evaluable for DLTs and will be replaced.

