15.2 Study Design/Objectives

The proposed clinical trial is a phase 1b/2a, open-label, multicenter study of the administration of atezolizumab (MPDL3280A) in combination with NT-I7 in patients with anti-PD-1/PD-L1 naïve or relapsed/refractory high-risk skin cancers: cSCC, MCC and melanoma.

This study will evaluate the safety and anti-tumor activity of NT-I7 in combination with atezolizumab, including estimation of the MTD and/or the RP2D. The trial is designed to

determine whether NT-I7, at doses known to increase the peripheral blood T-cell level, will also increase the level of tumor infiltrating T-cells and thereby increases the efficacy of atezolizumab.

15.2.1 *Dose Escalation Phase*

A 3+3 dose escalation design will be utilized. Four pre-specified doses of NT-I7 (120, 360, 840, and 1200 µg/kg) will be tested (refer to Section 5). The initial dose level will start at 120 µg/kg. NT-I7 doses will be escalated according to the dose escalation scheme in Section 5.2.2, 1200 µg/kg as the MAD. Enrollment will continue until the MTD or RP2D is identified, or up to the MAD.

The RP2D will be selected according to the following logic, taking into account the MTD determination from the Dose Escalation Phase (Phase 1b) and the MED level which is defined as the dose level at which maximum effects on peripheral blood T-cell levels and intratumor T-cell levels are observed. The intratumor T-cell levels will dominate if the peripheral blood and intratumor T-cell levels differ. The available data will be assessed by the Data and Safety Monitoring Committee, which includes the ION Coordinating Center, the Protocol PI, clinical sites PIs and NeoImmuneTech's Chief Medical Officer or designee to select the RP2D.

- If the MTD is determined AND
 - MTD = MED, then the RP2D = MTD = MED
 - MTD > MED, then the RP2D = MED
- If the MTD is not reached, then the RP2D = MED
- Once the RP2D has been selected, the trial will proceed to the Dose Expansion Phase (Phase 2a) to further evaluate RP2D in a larger number of patients.

15.2.2 *Expansion Phase*

The selected RP2D will be further evaluated in the Phase 2a.

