Based on the available data provided in Section 2.2, the average historical ORR for the patients in this study would be 45.25% in Arm I and less than 5% in Arm II. With a total of 24 patients treated at the RP2D in Phase 2a of the study in Arm I, the 95% confidence interval for an observed ORR of 17/24 or higher would exclude 45.25%. With a total of 36 patients treated at the RP2D in Phase 2a of the study in Arm II, the 95% confidence interval for an observed ORR of 6/36 or higher would exclude 5%.

Approximately 84 patients will be enrolled in this study; up to approximately 24 patients in the Phase 1b and approximately 60 evaluable patients in the Phase 2a of the study. The expected accrual is 4 patients per month total at approximately 8 ION sites.

Safety Population: All patients who receive at least 1 dose of the investigational regimen will be considered evaluable for safety and included in the overall safety analysis. For the Phase 1b, in the absence of a DLT, patients must complete the full 3-week DLT window period to be considered evaluable for DLTs. Patients who discontinue from the study before the completion of the full 3-week (21 days) DLT window for reasons other than the occurrence of a DLT (e.g., withdrawal of consent, rapid tumor progression, death due to rapid tumor progression, AE that does not meet DLT criteria) will not be considered evaluable for DLTs and will be replaced.

Efficacy Population: The efficacy analysis for the Phase 1b (dose escalation) portion will be conducted on all DLT-evaluable patients, as defined in Section 6.2.2. The efficacy analysis for the Phase 2a (expansion phase) portion will be conducted on all patients who received at least one cycle of study treatment and have at least one evaluable post baseline tumor assessments.

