3.1.1. Safety Population

The Safety Population will include all patients who receive at least 1 dose of the investigational regimen. The Safety Population will be the primary set for the analysis of safety and non-efficacy data.

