5. CHANGES TO PLANNED ANALYSES

Due to the premature closure of the study the following changes are made in comparison to the protocol:

- AEs leading to withdrawal and DLTs will not be listed separately.
- Laboratory values will only be listed.
- irRC (iRECIST) will not be summarized.
- Efficacy summaries will be performed on Efficacy Population only.
- All phases will be summarized within the same table.
- Duration of Stable Disease will replace Duration of Response analysis, due to limited patient responses.

Sponsor:	NeolimmuneTech, Inc.		
Protocol:	NIT-106 (ION-02)		
Document Version No.:	1.0	Document Date:	20Nov2023

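### DLTs are a Phase 1b primary endpoint, but no output described in the SAP text counts them by dose level

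*SAP*

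**What the plan says.** Protocol Section 3 (Table 2) places "Incidence and nature of DLTs" beside adverse event incidence and severity under the primary objective, which includes estimating the MTD and/or RP2D.

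The protocol also says who counts. Section 6.2.2 states: "The patients must complete the full 3-week DLT window to be considered evaluable for DLTs". Patients who leave early for reasons other than a DLT are not evaluable and are replaced (6.2.2, 6.8, 15.3). The protocol uses the same set a second time: in 15.3 the Phase 1b efficacy analysis "portion will be conducted on all DLT-evaluable patients, as defined in Section 6.2.2".

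The SAP keeps the primary safety objective (1.2.1) and defines a DLT (4.2.13). Its populations are Safety, Efficacy and PK. On the first of these, SAP 3.1.1 says: "The Safety Population will be the primary set for the analysis of safety and non-efficacy data". Section 5, giving early closure of the study as the reason, lists this change first: "AEs leading to withdrawal and DLTs will not be listed separately".

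**The concern.** A 3+3 escalation is decided by one statistic, the number of evaluable patients with a DLT at each dose level. If the SAP is followed as written, the described outputs contain neither that number nor its denominator. A reader of the study report could see adverse events by dose but could not check the MTD statement, or the safety part of the case for 1200 µg/kg, against the escalation rule. The Section 5 change is disclosed, but disclosing that an output is dropped does not supply the primary result.

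**Working it through.** **Plan's own figure.** Protocol 15.2.1 has "Four pre-specified doses of NT-I7" (120, 360, 840 and 1200 µg/kg). Protocol 1.2 gives the cohort size as "n=3 or 6 based on the 3+3 study design". So 4 × 6 = 24, which reproduces "up to approximately 24 patients will be enrolled in the Phase 1b" in Protocol 5.1, and 24 + 60 = 84 reproduces the total. A DLT table would have four rows, each with 3 or 6 evaluable patients.

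**Does any SAP population match the evaluability rule?**

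| SAP set | Entry rule | Match? |
|---|---|---|
| Safety (3.1.1) | At least one dose | No. It keeps patients who left before Day 21 without a DLT. |
| Efficacy (3.1.2) | At least one cycle and one evaluable post-baseline tumour assessment | No. The first scan is due at 9 ± 1 weeks (Protocol 6.7), so a patient can complete the window and still be left out. |
| PK (3.1.3) | At least one dose and one PK sample | No. |

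Result: 0 of 3.

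**Does any described output count DLTs?**
- SAP 2.5.3 names adverse events, laboratory tests, physical examination, vital signs, ECG and ECOG status, but not DLTs.
- SAP 4.2.13 is a definition with no output attached.
- SAP 4.11.1 tabulates events by grade, relatedness, seriousness, special interest, effect on dosing and death. DLTs are not among them.
- SAP 5 removes the separate listing.

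Result: 0 outputs. The other item in the same Section 5 bullet fares differently. Events leading to withdrawal lose their listing but keep a table in 4.11.1; DLTs keep nothing.

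**Can DLTs be read from the outputs that remain?**
- *Window.* A DLT falls in Days 1 to 21 (Protocol 6.2). Treatment-emergent events run to 30 days after the last dose (SAP 4.11.1).
- *Overcount.* Grade ≥3 lymphocytopenia and Grade 3 lymphocyte increase are not DLTs (6.2.1), and several Grade ≥3 events are exempt depending on duration or management (6.2.2). All would enter a Grade ≥3 table.
- *Undercount.* Grade 2 bilirubin can be a DLT (6.2.1), and a Grade ≥3 table misses it.
- *Judgement.* Expected toxicities attributed entirely to atezolizumab are excluded, and the final decision follows consultation with the coordinating centre and protocol PI (6.2). The SAP text mentions no flag recording that decision.

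**What the missing table would hold.** Exact (Clopper-Pearson) 95% limits for x DLTs in n patients are Beta(0.025; x, n − x + 1) and Beta(0.975; x + 1, n − x). The lower limit is 0 when x = 0.

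| DLTs / evaluable | Rate | 95% CI |
|---|---|---|
| 0/3 | 0% | 0 to 70.8% |
| 0/6 | 0% | 0 to 45.9% |
| 1/6 | 16.7% | 0.4 to 64.1% |
| 2/6 | 33.3% | 4.3 to 77.7% |

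These widths belong to any 3+3 cohort and are not a cost of the omission. They show how little data each row carries. The step from 1/6 to 2/6, a single patient, is the step from escalating to stopping.

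**The case against.** The strongest defence is that Section 5 drops only a separate listing. All adverse events are still listed by patient, Phase 1b is presented by dose level (SAP 4.2.1), and adverse event incidence and severity, also a primary endpoint, remain tabulated. The SAP refers to table shells and to an Appendix A with the DLT criteria. Neither is in the text available, so a DLT row or flag there cannot be ruled out. This stands as a limit on the claim: a reader might infer that DLTs will never be reported, and the documents do not go that far. It does not supply a count. The listings would let someone attempt a reconstruction, but not recover the adjudicated decisions.

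A reader might also infer that the RP2D is left without support. That is too strong. Under Protocol 5.2.2 the RP2D equals the MED when the MTD is not reached or exceeds it, and the MED is defined by T-cell levels. Escalation decisions went through the Data and Safety Monitoring Committee and were documented to sites. The dose was fixed in Amendment 5 (19JAN2023), before the SAP (20Nov2023). The omission affects reporting and could not change the dose decision.

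Finally, one might measure the harm by a shifted denominator, such as 1/6 becoming 1/8 (12.5%) if two replaced patients were counted. The documents report no replacements, and the SAP plans no DLT rate on the Safety Population, so that is not a measure of harm.

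Early closure is a fair reason for replacing duration of response when responses are few. It does not explain this cut, because Protocol 5.3 says the escalation phase had already produced the RP2D.

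**Conclusion.** The point holds for the SAP text. A primary endpoint has a definition but no described output (0), and no analysis set that fits it (0 of 3). The ordinary adverse event outputs do not replace it, because DLT status depends on window, relatedness, exceptions and adjudication. What is lost is the per-cohort count behind the MTD finding and the safety side of the RP2D choice.

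This assumes that the table shells and Appendix A, which could not be seen, add no DLT output. If a shell already carries DLT counts by dose level on the protocol's denominator, what remains is the missing population definition and a Section 5 bullet that should be brought into line. The documents do not support saying that DLTs are concealed or that the chosen dose is wrong. Because a primary endpoint is involved and the remedy is small, it should be corrected before the report outputs are final.

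**What to change.** 1. Add a DLT-Evaluable Population to SAP 3.1, following the wording of Protocol 15.3: patients with a DLT count as evaluable, and patients without one must complete the 21-day window. The sentence quoted from 6.2.2 should not be copied alone, since it would exclude a patient whose DLT ended participation early.
2. Add one Phase 1b table by dose level with the numbers treated, evaluable, replaced and with a DLT (n/N). An exact 95% interval is optional, because the escalation rule works on counts. Keep Phase 2a patients at 1200 µg/kg out of this table; Section 5 otherwise puts all phases in one table.
3. Add a short by-patient DLT listing, or a DLT flag in the adverse event listing, to cover the nature of the events.
4. Remove DLTs from the first bullet of SAP Section 5.

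The cost is SAP wording, one small table and one listing or flag for at most about 24 patients. Protocol 6.2.2 already requires sites to notify the protocol PI and coordinating centre of each DLT, so no new data collection should be needed.

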Overall response will also be assessed using iRECIST. Immunotherapeutics may result in infiltration of immune cells leading to transient increase in the size in malignant lesions, or undetectable lesions becoming detectable. The criteria are identical to those of RECIST 1.1 in many respects but have been adapted to account for instances where an increase in tumor burden, or the appearance of new lesions, does not reflect true tumor progression.

Key differences are described below. All responses defined using iRECIST criteria are designated with a prefix. iRECIST best overall responses will be recorded separately.

Confirming progression: Unlike RECIST 1.1, iRECIST requires the confirmation of progression and uses the terms iUPD (unconfirmed progression) and iCPD (confirmed progression). Confirmatory scans should be performed at least 4 weeks, but no longer than 8 weeks, after iUPD.

iCPD is confirmed if further increase in tumor burden, compared to the last assessment, is seen as evidenced by one or more of the following:

- Continued increase in tumor burden (from iUPD) where RECIST 1.1 definitions of

- progression had been met (from nadir) in target, non-target disease, or new lesions.
- o Progression in target disease worsens with an increase of at least 5 mm in the absolute value of the sum.
 - o Continued unequivocal progression in non-target disease with an increase in tumor burden.
 - o Increase in size of previously identified new lesion(s) (an increase of at least 5 mm in the absolute value of the sum of those considered to be target new lesions) or additional new lesions.
- RECIST 1.1 criteria are met in lesions types (target or non-target or new lesions) where progression was not previously identified, including the appearance of additional new lesions.

If iUPD is not confirmed at the next assessment, then the appropriate response will be assigned (iUPD if the criteria are still met, but no worsening, or iSD, iPR, or iCR if those criteria are met compared to baseline). The prior documentation of iUPD does not preclude assigning iCR, iPR, or iSD in subsequent time-point assessments or as best overall response (BOR) providing that iCPD is not documented at the next assessment after iUPD (*Lancet Oncol* 18:e143-e152, 2017 - Table 2).

New lesions:

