iUPD	iUPD	Yes	iUPD	Remains iUPD unless iCPD confirmed based on further increase in: 
 previously identified T lesion iUPD ≥ 5 mm and/or previously identified NT lesion iUPD (need not be unequivocal) and/or size or number of new lesions previously identified
Non-iUPD/PD	Non-iUPD/PD	Yes	iUPD	Remains iUPD unless iCPD confirmed based on increase in size or number of new lesions previously identified.

Time-point (TP) iResponse

Target Lesions*	Non-Target Lesions*	New Lesions*	Time Point Response	
			No prior iUPD**	Prior iUPD**, ***
* Using RECIST 1.1 principles. If no PSPD occurs, RECIST 1.1 and iRECIST categories for CR, PR, and SD would be the same. ** in any lesion category. *** previously identified in assessment immediately prior to this TP.				

All patients will have their iBOR from the start of study treatment until the end of treatment classified as outlined below.

iRECIST best overall response (iBOR)

TPR 1	TPR 2	TPR 3	TPR 4	TPR 5	iBOR
iCR	iCR, iPR, iUPD, NE	iCR, iPR, iUPD, NE	iUPD	iCPD	iCR
iUPD	iPR, iSD, NE	iCR	iCR, iPR, iSD, iUPD, NE	iCR, iPR, iSD, iUPD, iCPD, NE	iCR
iUPD	iPR	iPR, iSD, iUPD, NE	iPR, iSD, iUPD, NE, iCPD	iPR, iSD, iUPD, NE, iCPD	iPR
iUPD	iSD, NE	PR	iPR, iSD, iUPD, NE	iPR, iSD, iUPD, iCPD, NE	iPR
iUPD	iSD	iSD, iUPD, NE	iSD, iUPD, iCPD, NE	iSD, iUPD, iCPD, NE	iSD
iUPD	iCPD	Anything	Anything	Anything	iCPD
iUPD	iUPD	iCPD	Anything	Anything	iCPD
iUPD	NE	NE	NE	NE	iUPD

Table assumes a randomized study where confirmation of CR or PR is not required.

- NE = not evaluable that cycle.
- Designation "I" for BOR can be used to indicate prior iUPD to aid in data interpretation.
- For patients with non-target disease only at baseline, only CR or non-CR/non-PD can be assigned at each TPR but is not shown in the table for ease of presentation.

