15. STATISTICAL CONSIDERATIONS

This section outlines the statistical analysis strategy and methods for the study. If, after the study has begun, but before the conduct of any analysis, changes are made to primary and/or key secondary hypotheses or the statistical methods related to those hypotheses, then the protocol will be amended (consistent with ICH Guideline E-9). Changes to exploratory or other non-confirmatory analyses made after the protocol has been finalized, along with an explanation as to when and why they occurred, will be listed in the Clinical Study Report (CSR) for the study. Post hoc exploratory analyses will be clearly identified in the CSR. No separate Statistical Analysis Plan (SAP) will be issued for this study.

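### The SAP alone drops the iRECIST component of the Phase 2a primary ORR, and the protocol's iRECIST best-response table contradicts the confirmed-response endpoint

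*SAP*

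**What the plan says.** Protocol Section 3, Table 2, gives the objective: "Phase 2a: To evaluate the Objective Response Rate (ORR) according to RECIST v1.1 and iRECIST, as determined by the investigator". The matching endpoint is the percentage of patients with "at least one confirmed partial response (PR) or complete response (CR) according to RECIST v1.1 and iRECIST". The synopsis states the same objective. Protocol 11.1 then makes RECIST 1.1 the primary measure of response and adds iRECIST as a further evaluation. Protocol 11.1.5 asks for best response under iRECIST to be captured apart from the RECIST 1.1 result.

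SAP 2.5.1 and 4.8.1 define ORR as confirmed response by RECIST v1.1 only. SAP Section 5 opens with "Due to the premature closure of the study the following changes are made in comparison to the protocol" and lists "irRC (iRECIST) will not be summarized". SAP 4.8.2 nevertheless defines PFS by RECIST v1.1 and irRC.

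On changes, Protocol 15 says that if, after the start and before any analysis, "changes are made to primary and/or key secondary hypotheses or the statistical methods related to those hypotheses, then the protocol will be amended". It also says that there will be no separate SAP.

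On the iRECIST rules, a note under the best-overall-response (iBOR) table in Protocol 11.1.5 reads "Table assumes a randomized study where confirmation of CR or PR is not required". For progression, the same section says "Confirmatory scans should be performed at least 4 weeks, but no longer than 8 weeks, after iUPD", where iUPD is unconfirmed progression.

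**The concern.** A component named in the primary endpoint leaves the planned summaries through a SAP written after the study had closed. Early closure explains why an analysis might be simplified. It does not explain why one criterion is left out when the protocol already asks for the data.

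If the iRECIST results are later listed or published, two defects in the protocol matter. The iBOR table credits a response without confirmation, so site-recorded iBOR need not match the endpoint. The window for confirming progression does not fit the imaging schedule, so it is unclear when confirmed progression (iCPD) should be called.

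**Working it through.** **1. The plan's own ORR figures.** Protocol 15.3 and SAP 4.1 say that 17/24 in Arm I excludes 45.25% and 6/36 in Arm II excludes 5%. The exact (Clopper-Pearson) 95% lower limit is the 2.5% point of Beta(r, n−r+1).
- 17/24: 48.9% to 87.4%, excludes 45.25%. 16/24: 44.7% to 84.4%, does not.
- 6/36: 6.4% to 32.8%, excludes 5%. 5/36: 4.7% to 29.5%, does not.

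Both thresholds are reproduced. Neither document says which criterion supplies the numerator.

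**2. Weight of one patient who responds by iRECIST only.** At planned arm sizes, 1/24 = 4.2 points and 1/36 = 2.8 points. Early closure makes the real denominators unknown here; smaller ones would raise both figures.

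**3. Confirmation of response.** The passages side by side:
- Table 2: response must be confirmed under both criteria.
- Protocol 5.1: the trial is non-randomized.
- Protocol 11.1.4.3, table footnote: confirmation applies to non-randomized trials whose primary endpoint is response. Phase 2a is such a trial.
- Protocol 11.1.5, iBOR table: confirmation is not needed. Its first row scores iCR when an initial iCR is followed only by non-evaluable or iUPD readings. Its third row scores iPR when one iPR is followed by iSD.

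So the iBOR table contradicts the other three. The documents give no share of unconfirmed responses, so the effect can only be shown over an assumed range. Hold the confirmed rate at the historical p0 and let a share u of first responses go unconfirmed. The observed rate is p0/(1−u), and the chance of reaching the threshold is P(X ≥ r | n, p0/(1−u)).

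| u (assumed) | Arm I rate | P(≥17/24) | Arm II rate | P(≥6/36) |
|---|---|---|---|---|
| 0% | 45.25% | 1.0% | 5.00% | 0.8% |
| 10% | 50.28% | 3.4% | 5.56% | 1.4% |
| 20% | 56.56% | 11.3% | 6.25% | 2.3% |
| 30% | 64.64% | 34.4% | 7.14% | 4.1% |

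With confirmation required, the first line applies.

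**4. Confirmation of progression.** Protocol 11.1.5 gives 4 to 8 weeks after iUPD. Protocol 6.5 sends the follow-up scan to the next planned imaging visit, with a 4-week minimum and no maximum. Protocol 6.7 and the Study Calendar give 9 ± 1 weeks for the first two timepoints, then 12 ± 1.
- First to second scan: nominal 9 weeks. The range is 8 to 10 if the tolerance applies to the interval. If visits are anchored to Cycle 1 Day 1 (weeks 8–10 and 17–19), it is 17−10 = 7 to 19−8 = 11.
- Under anchoring, if both visits fall uniformly in their windows (an assumption), P(gap ≤ 8) = (2−1)²/(2×2²) = 1/8, about 12%.
- Later scans: nominal 12 weeks. The range is 11 to 13, or 10 to 14 if anchored.

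The 8-week limit is missed at nominal timing, reachable only at the early edge for the first pair, and never met by scans run at the 12-week interval. The Study Calendar has no separate confirmatory visit.

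**The case against.** The best defence is that Protocol 11.1 ranks RECIST 1.1 first, the SAP keeps that confirmed rate, and the omission is openly listed with a reason. All of that stands. A reader might infer that half of the primary endpoint has been lost; the ranking in 11.1 does not support that. What remains is a conflict within the protocol, because Table 2 names both criteria without ranking them.

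A reader might also infer selective reporting, since SAP Section 5 refers to limited responses when it replaces duration of response, so something was known about outcomes. The documents do not support that inference. Protocol 11.1.5 notes that the two criteria give the same response categories unless pseudo-progression occurs, and in that case iRECIST can credit a later response. Leaving it out removes the more permissive count and is unlikely to flatter the result.

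It can be said, too, that Phase 2a is descriptive, with no p-values (SAP 4.2.5), so the amendment rule is not engaged. That is arguable. But ORR by both criteria is the stated Phase 2a primary endpoint, and Protocol 15 reserves the simpler route, a note in the study report, for exploratory or other non-confirmatory analyses.

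Finally, while iRECIST is not summarized, neither the iBOR note nor the progression window changes a planned table. That also stands, and it limits the weight of both.

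**Conclusion.** The point holds in a limited form. A named component of the primary endpoint is dropped by the SAP alone, with no covering amendment in the supplied documents, and SAP 4.8.2 was not brought into line. The iBOR table contradicts the endpoint it would serve.

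Three stronger readings fail:
- That iRECIST response needs no confirmation in this trial: Table 2 does require it, so this is a contradiction to resolve.
- That the scans can never meet the window: the first pair can at its early edge, and Protocol 6.7 sets a recommended schedule whose later scans may come sooner.
- That the window misclassifies ORR: Protocol 11.1.5 still allows iCR, iPR or iSD when progression is not confirmed at the next assessment. The effect is mainly on when iCPD is called.

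The size is 4.2 or 2.8 points per iRECIST-only responder at planned arm sizes. The table of assumed unconfirmed shares shows sensitivity only; it is not an estimate. All of this assumes that iRECIST responses were recorded as Protocol 11.1.5 asks.

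**What to change.** - Add one row to the SAP ORR table: confirmed ORR per iRECIST as n/N, in the SAP's pooled dose groups and by Phase 2a arm, as Protocol 15.5.1 specifies.
- If it is still omitted, list iBOR by patient and report the omission in the study report as a change to the primary endpoint.
- State which criterion is primary, so that Table 2 and Protocol 11.1 agree.
- Replace the note under the iBOR table so that iCR or iPR counts toward ORR only when confirmed, and derive confirmation from the recorded timepoint responses. The 11.1.4.3 table already uses more than 4 weeks for RECIST 1.1, and the routine on-treatment gaps above are all at least 7 weeks.
- Make SAP 4.8.2 consistent with SAP Section 5.
- The sponsor should reconcile the window in Protocol 11.1.5 with Sections 6.5 and 6.7 and the Study Calendar, and say how the analysis treats confirmation outside it. Because Section 6.5 ties that scan to treatment beyond progression, the choice of rule is not made here.

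The cost is one table row, a few sentences and a small programming effort for few responders. The by-arm split is an addition to the SAP's pooled layout.
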